10.6.2 Columbia-Suicide Severity Rating Scale (C-SSRS)

No statistical testing will be performed on C-SSRS. The number and percentage of subjects reporting any suicidal ideation and any suicidal behavior will be summarized descriptively by treatment group. Shift table of C-SSRS maximum severity of suicidal ideation/behavior compared to baseline will be provided by treatment group.

10.6.3 Laboratory Test Results

Shifts tables of the laboratory toxicity for selected lab analytes (alanine aminotransferase, aspartate aminotransferase, alkaline phosphatase, total bilirubin, creatinine) based on Common Terminology Criteria for Adverse Events (CTCAE) grade (version 4) relative to baseline will be tabulated by treatment group for entire study

period. In the cases when CTCAE grading scales include numeric ranges in combination with clinical assessment (eg, Potassium [Hypokalemia]), laboratory test results may be summarized based on standard normal ranges or by CTCAE grade utilizing investigator's input.

Summary of change from baseline for absolute neutrophil count (ANC), alanine transaminase (ALT), aspartate aminotransferase (AST) and creatinine will also be provided.

Additional liver test summary table will provide the number and percentage of subjects by treatment group for the following categories:

- AST and ALT (> 3x ULN; > 5x ULN; > 10x ULN; > 20x ULN respectively)
- AST or ALT (> 3x ULN; > 5x ULN; > 10x ULN; > 20x ULN respectively)
- Total Bilirubin (> 1x ULN; >1.5x ULN; >2x ULN respectively)
- ALP (>1.5 ULN)
- ALT or AST > 3x ULN and Total Bili \geq 2x ULN and ALP < 2x ULN

10.6.4 Vital Signs

Descriptive summaries of blood pressures and HR will be provided at baseline and at each study visit. In addition, blood pressures and HR collected during ETTr will be summarized at specific time points (baseline, peak and last measurement). Descriptive summaries will be provided for the maximum change from baseline in SBP and HR on day 1 post dose during ETTr for Country Specific Supplement countries.

10.6.5 Antibody Formation

The incidence and percentage of subjects who develop anti-AMG334 antibodies (binding and if positive, neutralizing) at any time will be tabulated by treatment group.

10.6.6 Exposure to Concomitant Medication

Number and proportion of subjects receiving therapies of interest will be summarized by category for each treatment group as coded by the World Health Organization Drug (WHODRUG) dictionary. See [Appendix D](#) for a list of selected medications and their groupings.

10.7 Pharmacokinetic Analysis

All PK-related tables, figures, listings and other deliverables will be generated by PKDM. Serum AMG 334 concentrations will be summarized using descriptive statistics.

Appendix A. Post-baseline Study Visits

Since the actual visit for a subject may not exactly coincide with their targeted visit date, the actual visit date is mapped to the study visit as following. The study day window will be utilized to define study visit for labs, antibody, vital signs and physical measurements collected at office visits.

Study Visit	Target Day	Study Day
Week 4	29	16-43
Week 8	57	44-71
Week 12	85	72 to Min (EOS Date, last IP dose date + 84 days)

Note:

1. If more than one visit (including unscheduled visits, ie, CPEVENT = 'UNSCHED') fall within the same defined window, scheduled visit will be used regardless of the distance from the target day. Unscheduled visit will only be used when there is no scheduled visit in the defined window. The closest visit to the target day among the same type of visit (scheduled vs. unscheduled) will be considered for analysis. If two assessment dates are equidistant from the target date, the latter visit will be considered for analysis.
2. For Country Specific Supplement countries, CSSRS and ECG data are collected at week 2 (target day 14), corresponding to study day 1-28.

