### 7.1 Schedule of Assessments

Product: Erenumab (AMG 334)  
 Protocol Number: 20140254  
 Date: 28 October 2016

Page 25 of 63

Table 1. Schedule of Assessments

Procedure	Screening Period (up to 6 weeks) Screening Visits				On-Study Period (12 weeks) On-Study Visits l					EOS/ET	
	Visit 1 a	Visit 2 a	Visit 3	Visit 4 l	Day 1		Week 2 l	Week 4	Week 8		Week 12
					Pre-dose b	Post-dose					
General and Safety Assessments											
Informed Consent	X										
Physical Examination, including weight	X									X	
Targeted Medical/Surgical History	X										
Height	X										
Randomization c					X						
Columbia-Suicide Severity Rating Scale	X				X			X	X	X	
ETT d		X d	X d	X d		X					
Blood Pressure, Heart Rate e	X				X	X		X	X	X	
ECG	X										
Concomitant Medications	X				Record Continuously					X	
Serious Adverse Events	X				Record Continuously					X	
Adverse Events and Disease Related Events						X	Record Continuously			X	
Collection of Events for Adjudication						X	Record Continuously			X	
Angina diary l	X				Record Continuously					X	
Laboratory Assessments											
Hematology, Chemistry (central laboratory)	X				X					X	
Hepatitis Sample Collection	X										
Urine pregnancy test g (females of reproductive potential)	X				X					X	
Pharmacokinetic Sampling						X h					
Biomarker Sampling					X						
Urine drug screen k	X										
Dosing											
AMG 334 or Placebo						X					

Footnotes defined on [next page](#)

Product: Erenumab (AMG 334)  
Protocol Number: 20140254  
Date: 28 October 2016

Page 26 of 63

ECG = electrocardiogram; EOS = end of study; ET = early termination; ETT = Exercise Treadmill Test; PK = pharmacokinetic.

a Visits 1 and 2 in the Screening period may be combined. In the case where visits 1 and 2 are combined, all visit 1 assessments must be completed prior to the ETT for visit 2. The laboratory assessment results do not need to be reviewed prior to the ETT for visit 2, but must be reviewed prior to subsequent ETT (or before randomization).

b Pre-dose assessments should be conducted on day 1 prior to randomization.

c Week 1 begins on the date of randomization. Study day 1 is defined as the date investigational product is received.

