d During the screening period, two ETTs are required > 48 hours and ≤ 14 days apart that meet inclusion criteria, and they will be reviewed by a core ECG laboratory to confirm eligibility. No more than 3 ETTs can be performed during the screening period. Each ETT should occur within 14 days of each other and the total screening period for ETTs should not exceed 28 days.

e Blood pressure and heart rate should be assessed at all visits following the standard procedure. During ETT visits, the standard procedure will be conducted prior to the ETT; blood pressure assessments will also be conducted following the monitoring procedure described for the ETT.

f Angina diary will be completed by subjects beginning on the day of Visit 1 and through the EOS/ET visit to record angina episodes not occurring during ETTs.

g Results of pre-dose pregnancy test must be reviewed prior to administration of investigational product on day 1.

h PK sample to be drawn on day 1 after completion of exercise treadmill test post-randomization (ETTr).

i Visit at week 2 can be done via telephone contact.

j Study visit windows are ± 1 week.

k Urine drug screen may also be performed as needed throughout the study per investigator judgment.

l Optional Visit 4 to be performed if ETT3 is required for eligibility determination.

CONFIDENTIAL

AMGEN®

AMGEN®

---

Product: Erenumab (AMG 334)  
Protocol Number: 20140254  
Date: 28 October 2016

Page 27 of 63

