### **7.3.12 Laboratory Assessments**

All screening and on-study laboratory samples will be processed and sent to the central laboratory, unless otherwise noted. The results of this testing will be maintained in the source documents at the site. The central laboratory will provide a study manual that outlines handling, labeling, and shipping procedures for all samples. Please refer to the central laboratory manual for the complete listing of analytes run by the central laboratory. Blood samples will be obtained by venipuncture before investigational product administration, and PK sampling will be done postdose after ETT. The date and time of sample collection will be recorded in the source documents at the site. Specific analytes for serum chemistry, hematology, and other testing to be conducted on blood and urine samples are below ([Table 3](#)). Although not specifically listed, additional components, abnormal, and/or atypical cells will also be reported if present.

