#### **10.5.5 Safety Endpoints**

The SAS will be used to analyze safety endpoints based on the actual treatment received.

The Medical Dictionary for Regulatory Activities (MedDRA) will be used to code all adverse events.

Subject incidence of all treatment-emergent adverse events will be tabulated by treatment groups. Tables of fatal adverse events, serious adverse events, leading to withdrawal from investigational product, adverse events of special interest if any, and Disease Related Events also will be provided.

Subject incidence of Disease Related Events and fatal Disease Related Events will be tabulated by system organ class and preferred term.

The analyses of selected safety laboratory endpoints will include summary statistics over time by treatment group. Shift tables of the worst on-study safety laboratory toxicity based on grade relative to baseline will be tabulated by treatment group.

The analyses of vital signs will include summary statistics over time by treatment group.

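### SAP Appendix A assigns laboratory results to Week 4 and Week 8 windows in which no laboratory sample is scheduled, so any such rows would describe only selected subjects

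*SAP*

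**What the plan says.** **Schedule.** In Protocol Section 7.1, Table 1, the hematology and chemistry row is marked at Visit 1, Day 1 pre-dose and EOS/ET, and nowhere else. The schedule for the supplement countries (Supplement version 3) has the same three time points. Protocol Section 7.3.12 agrees: "Blood samples will be obtained by venipuncture before investigational product administration, and PK sampling will be done postdose after ETT".

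**Windows.** SAP Appendix A uses one window table for four kinds of data: "The study day window will be utilized to define study visit for labs, antibody, vital signs and physical measurements collected at office visits". Week 4 is Days 16-43 and Week 8 is Days 44-71. The Week 12 window is given as "72 to Min (EOS Date, last IP dose date + 84 days". Note 1 adds: "Unscheduled visit will only be used when there is no scheduled visit in the defined window".

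**Planned tables.** Protocol Section 10.5.5 plans laboratory summary statistics over time by treatment group, and SAP Section 10.1 calls for summaries at each visit. SAP Section 10.6.3 adds change-from-baseline summaries for ANC, ALT, AST and creatinine without naming visits. Separately, the protocol specifies "Shift tables of the worst on-study safety laboratory toxicity based on grade relative to baseline", and SAP Section 10.6.3 has these shifts "relative to baseline will be tabulated by treatment group for entire study" period. SAP Section 11 declares no change from the protocol's analyses.

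**The concern.** The window table gives laboratory results three post-dose time points, but the schedule supplies one. If the by-visit rule is followed as written, a Week 4 or Week 8 laboratory row can be populated only by subjects who had blood drawn for some particular reason, or who left early. Protocol Appendix A shows one such route: a subject with AST or ALT above 3 x ULN has liver tests repeated.

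A Week 4 ALT row could then consist largely of subjects sampled because something was suspected, next to a Week 12 row built on the scheduled sample. Read down the page, the difference between rows would look like a change over time when it reflects who was sampled.

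There is a second problem in the same table. The one scheduled post-dose sample can be lost from the by-visit summary, because the Week 12 window closes before the protocol's visit window does.

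**Working it through.** The plan gives no power or sample-size figure on this point. The check is study-day arithmetic.

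Inputs:
- Laboratory time points: Protocol Table 1 and the supplement schedule. The blood pressure row of the same table does carry marks at Weeks 4 and 8, so the blanks in the laboratory row are not a column shift.
- Windows and target days: SAP Appendix A.
- Dosing: a single dose on Day 1 (Protocol Section 6.2.1.1).
- Study-day convention: dates on or after Day 1 add 1 (SAP Section 6.2).
- Visit tolerance: "Study visit windows are ± 1 week" (Table 1 footnote).

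**Step 1, target days.** Target = 7 x week + 1, giving 29, 57 and 85. These match Appendix A.

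**Step 2, days the protocol permits.** Target ± 7.

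**Step 3, upper limit of Week 12.** Dose on Day 1 plus 84 days is Day 85. An EOS date before Day 85 closes the window sooner; a later one does not extend it.

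| Visit | Target | Protocol permits | SAP window | Scheduled laboratory samples |
|---|---|---|---|---|
| Week 4 | 29 | 22-36 | 16-43 | 0 |
| Week 8 | 57 | 50-64 | 44-71 | 0 |
| Week 12 (EOS/ET) | 85 | 78-92 | 72-85 | 1 |

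**Step 4, can the Week 12 sample reach an earlier window?** The earliest permitted day is 78, which is after 71. It cannot. Any Week 4 or Week 8 value must come from an unscheduled sample or an early-termination visit.

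**Step 5, does this depend on how note 1 is read?** The SAP does not say whether a scheduled visit is judged per assessment or per visit.
- Per assessment: nobody has a scheduled laboratory sample at Week 4 or 8, so any unscheduled sample in the window is used.
- Per visit: an attended Week 4 or Week 8 office visit blocks the unscheduled sample, so unscheduled values come only from subjects with no scheduled visit in that window.
- Under either reading, an early-termination sample may enter as a scheduled one.

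The subjects differ between the readings, but they are selected in each.

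**Step 6, the Week 12 gap.** Permitted days number 92 - 78 + 1 = 15. Days 86-92 lie beyond the window: 92 - 85 = 7 days. Example: with EOS on Day 88, min(88, 85) = 85, so the Day 88 sample belongs to no window although the visit was on time.

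**The case against.** The strongest reply is that no Week 4 or Week 8 laboratory table is named anywhere. Appendix A is a shared mapping rule and already exceeds the schedule for other data: antibody samples have no Week 8 time point, and weight is measured only at Visit 1 and EOS/ET. The general phrases about visits and time could be met by baseline and Week 12 alone. This stands in part: the misleading rows arise only if the by-visit rule is applied to laboratory data as written. But nothing in either document restricts it, and Appendix A names labs first among the data it maps.

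A reader might infer that unscheduled samples will always fill the Week 4 and Week 8 rows. The documents do not establish that. Note 1 is worded by visit, and subjects do have Week 4 and Week 8 office visits, so the literal reading blocks many of them. What survives is the narrower statement that whoever appears in those rows is selected.

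A reader might also infer that the worst-grade shift tables and the liver table are distorted and should be retitled as Week 12 tables. That is not supported. The shift tables cover the whole study period and do not use the windows. Keeping unscheduled values in a worst-value table preserves clinically detected abnormalities and is consistent with Protocol Section 10.5.5.

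Finally, laboratory results are not among the listed safety endpoints, and site staff and subjects stay blinded until the final analysis (Protocol Section 10.3). No bias between arms has been shown. Both points limit the weight of the concern without removing it.

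**Conclusion.** The point holds for the by-visit laboratory summaries. Scheduled post-dose hematology and chemistry samples number 0 in the Week 4 window, 0 in the Week 8 window and 1 in the Week 12 window. Rows for the first two could contain only unscheduled or early-termination samples, under either reading of note 1.

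How many subjects that would be cannot be calculated, because the documents give no rate of unscheduled laboratory sampling. That they would be few assumes such sampling and early termination are uncommon; that they would be selected does not depend on this.

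It is tempting to contrast these rows with a nearly complete Week 12 row. The documents do not support that either, since compliant samples on 7 of 15 permitted days fall outside the window. How many subjects would be affected depends on when they attend.

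The consequence is limited to descriptive laboratory tables. The primary and secondary efficacy analyses are not affected. The point concerns how results are summarised and does not call for further blood draws. It is worth correcting because the rule is explicit, would mislead if followed, and is easily changed.

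**What to change.** In SAP Appendix A and Section 10.6.3:

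1. Remove labs from the Week 4 and Week 8 windows. Limit by-visit laboratory summaries to baseline and Week 12/EOS, with change from baseline at Week 12/EOS only.
2. State that the scheduled/unscheduled rule in note 1 applies per assessment. Note 2 already treats C-SSRS and ECG separately, so a rule by type of assessment fits the format.
3. List unscheduled and early-termination laboratory samples by arm.
4. Reconcile the Week 12 upper limit (Day 85) with the protocol's visit window (to Day 92), for example by running the window to Day 92, so that the only scheduled post-dose sample is not dropped. Vital signs and antibody results share this window, so the change should cover them too.
5. Keep the entire-period worst-grade shift tables and the liver table, including unscheduled values. Add a footnote that only one post-dose laboratory sample was scheduled.

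The cost is SAP wording, one listing and a footnote. No new data are needed and no protocol-specified table is lost. Values removed from the by-visit rows remain in the listing and in the whole-period tables.

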### 7.2.3 End of Study Visit (Week 12/Early Termination Visit)

Subjects who complete the on-study period or who discontinue investigational product would complete the EOS/ET visit 12 weeks after the last dose of investigational product (refer to [Table 1](#)).

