6.2 Study Points of Reference

Study Day 1

Study Day 1 is defined as the first IP dose date. For subjects who are randomized but not dosed, Study Day 1 is defined as the date of randomization.

Study Day

Study Day is defined as the number of days from Study Day 1.

Before Study Day 1:

$$\text{Study Day} = (\text{Date of Interest} - \text{Date of Study Day 1})$$

On or after Study Day 1:

$$\text{Study Day} = (\text{Date of Interest} - \text{Date of Study Day 1}) + 1$$

Therefore the day prior to Study Day 1 is -1.

Post-baseline Study Visit

See [Appendix A](#).

Completing Study

A subject is defined as completing study if the primary reason for ending study is "Completed".

Completing Investigational Product (IP)

A subject is defined as completing IP if the reason for ending IP is "Completed".

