10.1 General Principles

The primary analysis to evaluate the effect of AMG 334 compared to placebo on exercise capacity in subjects with stable angina as measured by TET during an ETT.

The FAS will be used to tabulate demographic data, baseline disease characteristics, and subject disposition. The EAS will include all FAS subjects who received IP and completed the ETT and will be used to analyze the primary and secondary endpoints including the change from baseline in TET, time to onset of ≥ 1 mm ST-segment depression, and time to onset of exercise-induced angina. The Safety Analysis Set will be used to analyze safety endpoints.

Summary statistics by each treatment group will be tabulated at each visit. For continuous endpoints, descriptive statistics will be provided including number of subjects, mean, median, standard deviation, standard error, lower and upper quartiles, minimum, and maximum. For categorical endpoints, frequency, and percentage will be given. Missing data will not be imputed.

Baseline value for exercise duration is the average value of the two qualifying measurements in the screening period.

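### SAP Appendix A closes the Week 12 window on its target day (Day 85), so Week 12 visits on Day 86 to 92, which the protocol allows, map to no visit

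*SAP*

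**What the plan says.** SAP Appendix A states its scope: "The study day window will be utilized to define study visit for labs, antibody, vital signs and physical measurements collected at office visits". It gives three windows: Week 4 (target Day 29) covers Day 16 to 43; Week 8 (target Day 57) covers Day 44 to 71; Week 12 (target Day 85) covers "72 to Min (EOS Date, last IP dose date + 84 days"). Note 1 sets out how to choose when several visits fall in the same window. There is no later window, and no rule that returns an unmapped visit to its nominal label.

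SAP section 6.2 fixes the origin for dosed subjects: "Study Day 1 is defined as the first IP dose date". Days on or after that date are counted as the date difference plus one. Protocol section 6.2.1.1 and SAP section 3.1 specify a single dose.

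Protocol section 7.2.3 says that subjects "would complete the EOS/ET visit 12 weeks after the last dose of investigational product". Protocol Table 1, footnote j, adds: "Study visit windows are ± 1 week".

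The outputs that use the mapping include SAP section 10.6.4 ("Descriptive summaries of blood pressures and HR will be provided at baseline and at each study visit") and the general rule in SAP section 10.1 ("Summary statistics by each treatment group will be tabulated at each visit").

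**The concern.** A visit-mapping table should place every visit that the protocol accepts as on time. Here the upper limit for Week 12 looks as if it was carried over from the 84-day treatment-emergent period in SAP section 6.5. That limit serves a different purpose: it decides which events count as treatment-emergent. Used for visit mapping, it removes the whole late half of the allowed Week 12 window.

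Changes in vital signs are a listed safety endpoint (SAP section 4.1.3), and blood pressure and heart rate are to be summarised at each visit. The laboratory data are more exposed, because Week 12/EOS is the only scheduled post-dose haematology and chemistry draw in Protocol Table 1. A subject seen on Day 86 to 92 would have no scheduled post-baseline value in a laboratory summary by visit. Protocol section 10.5.5 asks for summary statistics over time for selected laboratory endpoints, and SAP section 11 declares no departures from the protocol's analyses. SAP section 10.6.3 then plans: "Summary of change from baseline for absolute neutrophil count (ANC), alanine transaminase (ALT), aspartate aminotransferase (AST) and creatinine will also be provided". It does not say whether that summary is by visit; if it is, it is affected too. Missing assessments are not imputed (SAP section 9.3), so nothing fills the gap.

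**Working it through.** **Inputs**
- Study Day on or after Day 1 = (date − date of Study Day 1) + 1 (SAP 6.2)
- One dose, so last dose date = first dose date = Study Day 1 (Protocol 6.2.1.1, SAP 3.1)
- Week 12/EOS visit 12 weeks after the dose (Protocol 7.2.3), with visits scheduled from Day 1 (Protocol 7.2.2)
- Visit window ± 7 days (Protocol Table 1, footnote j)
- Mapping windows from SAP Appendix A

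**1. Reproduce the SAP's target days.** Week 4: 28 + 1 = 29. Week 8: 56 + 1 = 57. Week 12: 84 + 1 = 85. All three match Appendix A.

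**2. Locate the cap.** Last dose date + 84 days = Study Day 84 + 1 = 85, which is the target day.

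**3. See whether the end-of-study date can extend it.** The subject-level end-of-study date is the date of the last protocol procedure (SAP 6.1). For a Week 12 visit on Day 88 it is Day 88 or later, and Min(88, 85) = 85. The end-of-study term can shorten the window but never lengthen it.

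**4. Compare the mapping windows with the protocol windows.**

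| Visit | Target | SAP window | Offset from target | Protocol window (± 7) | Permitted days unmapped |
|---|---|---|---|---|---|
| Week 4 | 29 | 16–43 | −13 / +14 | 22–36 | 0 of 15 |
| Week 8 | 57 | 44–71 | −13 / +14 | 50–64 | 0 of 15 |
| Week 12 | 85 | 72–85 | −13 / 0 | 78–92 | 7 of 15 |

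Day 78 to 85 is 8 of 15 days and maps correctly. Day 86 to 92 is 7 of 15 = 46.7% and maps to nothing.

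**5. Look for a rescue rule.** Note 1 of Appendix A chooses only among visits already inside a window. It can make matters worse: with an unscheduled visit on Day 80 and the scheduled Week 12 visit on Day 88, the unscheduled value is labelled Week 12 and the scheduled one is dropped.

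**6. Translate into subjects (assumption).** The documents give no distribution of Week 12 dates, so the share attending on Day 86 to 92 is unknown. Taking 10% to 50%:
- of 54 randomised: 0.10 × 54 = 5.4 to 0.50 × 54 = 27
- after the plan's own 5% dropout, 0.95 × 54 = 51.3: 0.10 × 51.3 = 5.1 to 0.50 × 51.3 = 25.7

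**7. Test the repair.** With a fixed upper bound of Day 92, all 15 permitted days map to Week 12. Day 99 does the same and gives 99 − 85 = +14, matching Weeks 4 and 8. Neither overlaps Week 8, which ends on Day 71.

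**The case against.** The arithmetic is hard to dispute; the counter-case is about size, intent and remedy.

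- **Size.** Seven of 15 counts calendar days, not subjects. The 10% to 50% range has no source in the documents, its top is slightly above what uniform attendance would give (46.7%), and the true figure could be near zero. This stands: the subject counts illustrate a range and should not be read as an estimate.
- **Intent.** The protocol ends safety event collection 12 weeks after the dose, and SAP section 6.5 uses the same 84 days. The cap may be deliberate alignment, and after a repair the Week 12 summaries could hold values from days on which a new adverse event would not count as treatment-emergent. That asymmetry is real, but it does not justify discarding an on-time scheduled visit, and Appendix A exists because visits miss their target dates.
- **Window.** Section 7.2.3 states no window for the EOS/ET visit. Footnote j is general, however, and most naturally covers Week 12.
- **Remedy.** Day 99 is a week beyond the last permitted day, and the +14 in the earlier windows serves to make them contiguous, which is not needed after the last visit. An unscheduled value on Day 93 to 99 could then fill an empty Week 12 slot. Only Day 92 follows directly from the protocol; Day 99 is workable because Note 1 still prefers scheduled visits.
- **Reach.** The affected tables are descriptive, with no test or decision rule attached, and vital signs are still summarised at Weeks 4 and 8. This stands and limits the consequence.

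**Conclusion.** The concern holds. As written, the Week 12 window cannot extend past Day 85, and 7 of the 15 days on which the protocol permits the visit (47%) map to no visit. The rule is wrong as stated, not merely short of detail. This rests on the single dose, the SAP's study day formula, and reading footnote j as covering the Week 12 visit.

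The clear loss is from the Week 12 blood pressure and heart rate summary; laboratory change from baseline is affected wherever it is tabulated by visit. The number of subjects cannot be derived from the documents; about 5 to 27 of 54 follows only from the assumed 10% to 50% late attendance.

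Not necessarily affected are the laboratory shift tables for the entire study period, the liver threshold table, antibody incidence at any time and the adverse event analyses. The primary and secondary endpoints, measured on the Day 1 treadmill test, are unaffected. The consequence is bounded, but the error is certain and should be corrected.

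**What to change.** In SAP Appendix A, replace the Week 12 window with Day 72 to 99, the same offsets as Weeks 4 and 8, or at least Day 72 to 92, which matches the protocol visit window. Remove the dose-date-plus-84-days cap for visit mapping only, and leave the 84-day treatment-emergent period in SAP section 6.5 as it is. Keep the upper bound a fixed day and do not tie it to the end-of-study date alone, so that later antibody follow-up samples under the country-specific supplement are not labelled Week 12.

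The cost is one cell in one SAP table. Data collection and study conduct do not change.
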